#### INVESTIGATIONAL PLAN SUMMARY

#### 1.0 BACKGROUND

#### 1.1 Device Name

The Preceptis Medical, Inc. Hummingbird TTS™ Tympanostomy Tube System (H-TTS)

#### **1.2** Device Description

The H-TTS is a disposable surgical tool designed to create an incision in the tympanic membrane and insert a ventilation tube (VT) in one pass down the ear canal, thereby reducing surgical trauma for the patient. The VT used with the HTTS is a standard, commercially available Armstrong-style ventilation tube. The H-TTS has received 510(k) clearance from the FDA under (i) general anesthesia in August 2014, (ii) for children under moderate sedation with local anesthesia in April 2015, and (iii) in-office in children 6-24 months old with local anesthesia in June 2020.

#### 1.3 Study Sites

There will be 4 study sites: St. Cloud ENT, the Mayo Clinic, Children's Hospitals and Clinics of MN, and the University of Minnesota Children's Hospital. St. Cloud ENT will enroll patients prospectively. Data from the other three sites will be retrospectively procured from the previous multi-site moderate sedation study using data that was not previously submitted to FDA in support of the 510k application for use of the H-TTS in children under moderate sedation (K142282). This clinical data was procured after K142282 had already been submitted.

#### 2.0 STUDY OBJECTIVE

The study is being initiated per section 522 of the Food and Drug Cosmetic Act (post-market surveillance). The objective of this study is continued commercial evaluation of the intraoperative safety and performance of the H-TTS for the placement of VT in patients undergoing a tympanostomy procedure under moderate sedation and local anesthetic.

#### 3.0 STUDY DESIGN

#### 3.1 Overview

The study will be a multi-site, prospective and retrospective, treatment-only post-market study of the H-TTS. The study will be performed in a commercial environment. Patients will already have a scheduled tympanostomy procedure with the H-TTS under moderate sedation and local anesthetic. A minimum of one hundred nine (109) subjects will be included in the study at 4 sites, one site prospectively (St. Cloud ENT) and three sites retrospectively (the Mayo Clinic, Children's Hospitals and Clinics of MN, and the University of Minnesota Children's Hospital).

#### 3.2 Timeline

- i. Expected enrollment completion date: Feb 2021
- ii. Expected date for final report submission Mar 2021

## 3.3 Data oversight and analysis

Data will be collected via an electronic data capture system (EDC) maintained by NAMSA, a contract research organization (CRO).

#### Sample size:

The sample size was chosen to ensure an adequate precision in the estimation of the conversion rate. Based on an expected conversion rate of 15%, a sample size of 109 subjects will provide an upper, one-sided, Wilson 95% confidence bound that is no more than 6% greater than the estimated conversion rate with a probability of approximately 0.80.

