## Poolability of prospective and retrospective patients:

Subjects from the previous multi-site moderate sedation study who were not included in the previous 510k (K142282) data will be included in this data analysis if they met the following criteria: children 6 months through 5 years of age, who are candidates for placement of VT and required use of the H-TTS under moderate sedation and accompanying local anesthetic.

Poolability of the subjects prospectively enrolled in the 522 study and those retrospectively procured through the multi-site conscious sedation study will be tested using Fisher's Exact test. The proportion of subjects requiring conversion will be analyzed in a 2x2 table where the rows consist of the study from which the subjects information came and the columns are whether or not the subject required conversion. If the p-value for this comparison is greater than 0.15, the data will be considered poolable for the purposes of statistical analysis.

In addition to assessing poolability of the conversion rates between sites, additional comparisons between the sites providing retrospective data and the site providing prospective data will be completed. Specifically, subject age, which is the only common demographic, will be compared between the combined data from sites supplying retrospective data and the site providing prospective data. Age data will be compared using a two sample Wilcoxon test.

An ad hoc analysis based on the outcome of any procedure that was converted will also be attempted. The outcome of converted procedures will be classified as successful or unsuccessful and the differences in successful outcomes will be compared between the sites providing retrospective data and the site providing prospective data. A Fisher's Exact Test will be used for this comparison. This analysis is done only on converted cases therefore it should be noted that the sample size for this analysis may be extremely small.

Rates will be calculated for the outcome variables and detailed summaries for all adverse events will be provided. Statistical summaries will include number, mean, standard deviation and range for continuous parameters or frequency and percent for categorical parameters. No formal statistical hypothesis tests are planned.

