## 6.0 SAMPLE SIZE

This study will include a minimum of 109 treated patients.

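### With 109 subjects and a 15% conversion rate, the Wilson upper bound lies within 6 points of the estimate with probability 0.15, not the stated 0.80

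*Combined protocol and SAP*

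**What the plan says.** The Sample size paragraph in section 3.3 gives every input. The planning rate is stated as "Based on an expected conversion rate of 15" per cent, and the size as "a sample size of 109 subjects". The precision promised is an "upper, one-sided, Wilson 95% confidence bound that is no more than 6% greater than the estimated conversion rate with a probability of approximately 0.80". Section 6.0 repeats the number: "This study will include a minimum of 109 treated patients". Section 3.1 gives the same minimum.

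The analysis text is the last paragraph under the poolability heading in section 3.3. It says that rates will be calculated, that categorical data will be summarised by "frequency and percent for categorical parameters", and that no formal hypothesis tests are planned. It does not mention a confidence bound.

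**The concern.** A Wilson interval is not centred on the observed proportion. Below 50% its centre is pulled upward, so the distance from the estimate to the upper bound is longer than the half-width. A sample size found by setting the half-width to 6 points will therefore not keep the upper bound within 6 points of the estimate. The plan measures from the estimate, so the stated probability looked too high.

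The study is for estimation only and is done under section 522, and the conversion rate is the first endpoint in section 4.0. The case for 109 subjects rests entirely on this precision sentence. If the sentence is wrong, the plan promises a precision that the study will usually miss, and anyone who recalculates it will find this.

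**Working it through.** **Inputs** (all from the Sample size paragraph, section 3.3): true rate 0.15; n = 109; one-sided 95% Wilson bound, so z = 1.645; margin 0.06 from the estimate; stated probability about 0.80. The 6% is read as percentage points, the reading most favourable to the plan; read as a relative 6%, the probability is about 0.

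**Formulas.** With p = x/n:

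- Wilson centre: C = (p + z²/2n) / (1 + z²/n)
- Wilson half-width: H = z·√[p(1−p)/n + z²/4n²] / (1 + z²/n)
- Upper bound: U = C + H
- Distance that the plan names: U − p = H + (C − p)

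For n = 109: z² = 2.7055, z²/2n = 0.01241 and 1 + z²/n = 1.02482.

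**Step 1: reproduce the plan's 0.80.** Compare H alone with 0.06. At x = 19, p = 0.1743 and H = 0.0596, which passes. At x = 20, H = 0.0607, which fails. For X ~ Binomial(109, 0.15), P(X ≤ 19) = 0.8036. The Wald margin z·√[p(1−p)/n] has the same cut-off (0.0598 at 19, 0.0610 at 20) and so the same probability. Searching upward from n = 95, 109 is the first size at which either criterion reaches 0.80. The stated figure is thus recovered for the half-width, not for the distance from the estimate.

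**Step 2: calculate the quantity the plan names.**

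| Conversions x | p | U | U − p (points) | H (points) | P(X ≤ x) |
|---|---|---|---|---|---|
| 12 | 0.1101 | 0.1692 | 5.91 | 4.96 | 0.150 |
| 13 | 0.1193 | 0.1798 | 6.05 | 5.13 | 0.226 |
| 16 | 0.1468 | 0.2111 | 6.43 | 5.57 | 0.529 |
| 19 | 0.1743 | 0.2418 | 6.75 | 5.96 | 0.804 |
| 20 | 0.1835 | 0.2519 | 6.84 | 6.07 | 0.866 |

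Worked through for x = 12: C = (0.1101 + 0.0124)/1.0248 = 0.1195, H = 0.0496, U = 0.1692, and U − p = 0.0591. The condition holds for x ≤ 12 and fails at 13. It holds again only for counts of 84 or more, whose probability is negligible. The probability is therefore P(X ≤ 12) = **0.150**.

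A check at the planning value: with p exactly 0.15, U = 0.2147, so the distance is 6.47 points. The condition fails at the rate on which the study was planned.

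**Step 3: try other readings** (one-sided 95% throughout):

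- Upper bound at or below 21%: 0.422
- Distance rounded to a whole per cent: 0.529
- Clopper–Pearson bound: 0.052
- Wilson with continuity correction: 0.027

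None gives 0.80.

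**Step 4: find what would be true.**

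- At n = 109, a margin of 6.8 points admits x ≤ 19 (6.75 points at 19, 6.84 at 20), with probability 0.804.
- For a margin of 6 points, the probability is 0.797 at n = 134, 0.787 at 135 and 0.838 at 136. The smallest n reaching 0.80 is 136.

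**The case against.** The arithmetic is not in dispute; the case against concerns weight.

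- **The practical gap is small.** The probability climbs steeply with the margin: 0.15 at 6.0 points, 0.53 at 6.5, 0.80 at 6.75 and 0.91 at 7.0. A shortfall of well under one point is less dramatic than 0.15 against 0.80 suggests. This stands, and the point should be read with it in mind.
- **No decision depends on the figure.** There is no performance goal, test or stopping boundary on the conversion rate, and section 4.1 says conversion is neither an adverse event nor an added risk. This also stands. But with no test planned, precision is the only rationale for the sample size, so a wrong precision figure leaves 109 without a correct justification.
- **The number 109 probably came from a sound half-width calculation that was then misdescribed.** The match in Step 1 makes this likely, though the documents do not confirm it. It would explain the error, but the sentence would still be wrong, because it measures from the estimate.
- **109 is a minimum.** More subjects would raise the probability, but about 27 more (136 − 109) would be needed.
- **The bound may be reported anyway.** The list of summaries is not exclusive, and the Sample size paragraph says the sample will provide the bound. This is fair: the plan does not exclude reporting it, but the analysis text does not commit to it.

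**Conclusion.** The concern holds. For the quantity the plan names, with 109 subjects and a true rate of 15%, the probability is 0.150 rather than about 0.80, so the promised precision would be missed about 85% of the time. Most misses would be small: the bound stays within 6.75 points of the estimate with probability 0.804. The sample size itself need not change; the statement supporting it must.

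The result rests on the plan's own inputs, on exact binomial sampling at a true rate of 15%, on the standard Wilson bound without continuity correction, and on reading 6% as percentage points. The absence of the bound from the analysis text is a minor reporting gap, and the conclusion does not depend on it.

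**What to change.** Keep 109 subjects and correct the Sample size paragraph in section 3.3, for example: *If the true conversion rate is 15%, 109 subjects give a one-sided 95% Wilson upper bound at most 6.8 percentage points above the observed rate with probability about 0.80.* Write percentage points, so that the margin cannot be read as relative.

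Add one sentence to the analysis text under the poolability heading: the conversion rate will be reported with its one-sided 95% Wilson upper bound.

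This costs wording only and no extra patients; the stated precision becomes slightly less favourable, 6.8 points instead of 6. There are two alternatives. The sponsor could keep the 6-point figure and relabel it as the half-width of the two-sided 90% Wilson interval, for which 0.80 is correct at 109. Or it could keep the sentence as written and raise the minimum to 136, which costs 27 more subjects and would also change sections 3.1 and 6.0.

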## Poolability of prospective and retrospective patients:

Subjects from the previous multi-site moderate sedation study who were not included in the previous 510k (K142282) data will be included in this data analysis if they met the following criteria: children 6 months through 5 years of age, who are candidates for placement of VT and required use of the H-TTS under moderate sedation and accompanying local anesthetic.

Poolability of the subjects prospectively enrolled in the 522 study and those retrospectively procured through the multi-site conscious sedation study will be tested using Fisher's Exact test. The proportion of subjects requiring conversion will be analyzed in a 2x2 table where the rows consist of the study from which the subjects information came and the columns are whether or not the subject required conversion. If the p-value for this comparison is greater than 0.15, the data will be considered poolable for the purposes of statistical analysis.

In addition to assessing poolability of the conversion rates between sites, additional comparisons between the sites providing retrospective data and the site providing prospective data will be completed. Specifically, subject age, which is the only common demographic, will be compared between the combined data from sites supplying retrospective data and the site providing prospective data. Age data will be compared using a two sample Wilcoxon test.

An ad hoc analysis based on the outcome of any procedure that was converted will also be attempted. The outcome of converted procedures will be classified as successful or unsuccessful and the differences in successful outcomes will be compared between the sites providing retrospective data and the site providing prospective data. A Fisher's Exact Test will be used for this comparison. This analysis is done only on converted cases therefore it should be noted that the sample size for this analysis may be extremely small.

Rates will be calculated for the outcome variables and detailed summaries for all adverse events will be provided. Statistical summaries will include number, mean, standard deviation and range for continuous parameters or frequency and percent for categorical parameters. No formal statistical hypothesis tests are planned.

Ad hoc analyses using logistic regression models will be used to assess the relationship between selected parameters and the outcome of conversion to general anesthesia. The prespecified parameters will be assessed individually in univariable models with a subset of these parameters being used in the multi-variate model. The pre-specified parameters are age, sex, weight, type of anesthesia/sedation, number of ears treated, surgeon experience, surgery duration, patient movement, anatomy and lack of visualization. After each parameter has been modelled univariately (stage 1), those parameters with a p-value less than 0.20 will be included in a multivariable model and a stepwise selection process will be employed to determine if any parameters have a statistically significant association with conversion. The nominal p-value for retention in the final reduced model will be 0.05.

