## 4.0 STUDY ENDPOINTS

4.1 The rate of conversion from moderate sedation to general anesthesia, along with surgeon experience, the patient and procedure characteristics associated with the decision to convert (age, sex, weight, type of anesthesia/sedation, number of ears treated, surgery duration (tympanostomy time for each ear), patient movement, anatomy, and lack of visualization). (Note: conversion to general anesthesia is not an adverse event, nor is it considered an additional risk to the patient.)

**4.2** The rate of intra-operative and pre-discharge AEs and rates for each specific type of event.

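### The plan commits to no confidence bound for the adverse-event rates, and names a bound for the conversion rate only in the sample-size rationale

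*Combined protocol and SAP*

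**What the plan says.** Section 4.0 sets two endpoints. Endpoint 4.1 is the rate of conversion to general anesthesia, with the characteristics associated with it. Endpoint 4.2 is "The rate of intra-operative and pre-discharge AEs and rates for each specific type of event".

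The sample-size paragraph of section 3.3 rests the choice of 109 subjects on the precision of an "upper, one-sided, Wilson 95% confidence bound" for the conversion rate. The margin is worded as "no more than 6% greater than the estimated conversion rate", to be met about 80% of the time if 15% of subjects convert. Section 6.0 makes 109 a minimum. No confidence bound is mentioned anywhere else in the document.

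What will be produced is stated at the end of the poolability text in section 3.3. Rates are to be calculated for the outcome variables, AEs are to be summarised in detail, and summaries are to include "frequency and percent for categorical parameters". The same paragraph says that no formal hypothesis tests are planned. The paragraph after it adds logistic models for factors associated with conversion.

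**The concern.** Section 3.1 describes a treatment-only study. With no comparator and no test of either endpoint rate, the study's statement on safety is an estimated rate, and an estimate needs a measure of its uncertainty. The plan names one for conversion, and there only to justify the sample size. For AEs it names none.

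This matters most when events are rare. Endpoint 4.2 asks for a rate for each type of event, and Attachment C lists three anticipated types, one of which is ossicular damage with hearing loss. Zero counts in some of these rows are plausible. A row reading 0 (0%) can be taken as absence of risk, when 109 children can exclude only rates above a few per cent.

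If the bound is added when the report is written, its method, sidedness and denominator will be chosen with the data in view.

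**Working it through.** **Inputs from the document.** n = 109 (section 6.0, a minimum). Expected conversion rate 15%, one-sided 95% Wilson upper bound, 6% margin, probability about 0.80 (section 3.3, sample size). z = 1.645.

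**Assumed inputs.** The document gives no expected AE rate, so 0 to 3 children with an AE out of 109 are used for illustration.

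**1. The plan's own figure.** Let X be the number of conversions, X ~ Binomial(109, 0.15), and p = X/n. The Wilson upper bound is

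U = [p + z²/(2n) + z·√(p(1−p)/n + z²/(4n²))] / (1 + z²/n).

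Its half-width, the distance from the Wilson midpoint to U, is z·√(p(1−p)/n + z²/(4n²)) / (1 + z²/n). This is 0.0596 at X = 19 and 0.0607 at X = 20, so it stays within 0.06 for X ≤ 19. P(X ≤ 19) = 0.8036, which reproduces the stated 0.80.

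If the 6% is read as worded, as the distance from the estimated rate to U, the condition holds only for X ≤ 12, and P(X ≤ 12) = 0.150. The stated 0.80 therefore matches a half-width of 6 points, or a distance above the estimate of about 6.75 points (0.0675 at X = 19). This is a side point, but it affects how the conversion bound will read once it is reported.

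**2. Conversion near the expected rate.** For 16/109, p = 0.1468, z²/(2n) = 0.0124, the square-root term is 0.0347 and 1 + z²/n = 1.0248. Then

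U = (0.1468 + 0.0124 + 1.645 × 0.0347) / 1.0248 = 0.211.

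The report would give 14.7% with an upper bound of 21.1%, a distance of 6.4 points.

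**3. AE rates.** The exact (Clopper-Pearson) one-sided 95% upper bound is the rate π at which P(X ≤ x) = 0.05, that is, the 95th percentile of Beta(x + 1, n − x). For x = 0 it is 1 − 0.05^(1/109) = 0.0271. Check: 0.9729^109 = 0.050.

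| Children with an AE, of 109 | Percentage reported | Exact upper bound | Wilson upper bound |
|---|---|---|---|
| 0 | 0% | 2.7% | 2.4% |
| 1 | 0.9% | 4.3% | 4.0% |
| 2 | 1.8% | 5.7% | 5.4% |
| 3 | 2.8% | 7.0% | 6.7% |

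**4. How easily a zero arises.** An event type with a true risk of 1% shows no cases in 109 children with probability 0.99^109 = 0.33. At a true risk of 2% the probability is 0.98^109 = 0.11.

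**5. Whether another analysis fills the gap.** The Fisher tests compare the two data sources on conversion and, among converted cases, on outcome. The Wilcoxon test compares ages. The logistic models estimate associations with conversion. None gives an interval for the conversion rate or for any AE rate.

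**The case against.** A reader might infer that the plan rules out a bound, or that the Wilson bound on conversion would not be reported. The document does not support either. The sentence on summaries says what they will include and is not an exhaustive list. Doing without hypothesis tests does not exclude intervals. The sample-size paragraph stands in the same section 3.3 and already names the rate, method, sidedness and level for conversion, so a fair reader would take that bound as intended. For conversion, the gap is a missing sentence in the analysis text.

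Two further objections have some force. The stated objective (section 2.0) is continued evaluation of intraoperative safety and performance, and the plan sets no precision target for AEs, so the study cannot be said to fail a goal that it set itself. Also, anyone with the count and the denominator can compute a bound, so no data are lost and no estimate is biased.

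What remains is endpoint 4.2. Nothing in the document states or implies a bound for it. That a reader could compute one does not replace a prespecified method in a study whose safety result is the estimate itself.

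**Conclusion.** The point holds as an absence of commitment. For the AE rates no bound is planned anywhere. For conversion a bound is implied by the sample-size rationale but not carried into the analysis text.

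The size depends on the count. At n = 109, 0, 1 or 3 children with an AE leave true rates up to 2.7%, 4.3% and 7.0% compatible with the data (exact, one-sided 95%). These figures rest on illustrative counts, on one outcome per child, and on pooled data at the minimum sample size. A larger sample would tighten the bounds. If the two data sources have to be shown separately, the bounds would be wider; the document does not give the split, so no figure is offered for that case.

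The omission does not invalidate the study. It does affect how its safety result would be read, and the plan should correct it.

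**What to change.** In the paragraph of section 3.3 that describes the summaries, add that:

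- the any-AE rate and each type-specific AE rate, per child, will be reported with an exact (Clopper-Pearson) one-sided 95% upper bound, including when the count is zero;
- the conversion rate will be reported with the one-sided 95% Wilson upper bound named in the sample-size paragraph;
- both will be given pooled when the plan's poolability rule (p greater than 0.15) is met, and by data source otherwise.

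Wilson would also serve for the AE rates; at 0/109 the two methods give 2.4% and 2.7%. What matters is that one is named in advance.

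The sample-size paragraph should at the same time say that the 6% is a half-width, or restate the distance above the estimate as about 6.75 points. Otherwise a reported 14.7% with a bound of 21.1% would appear to miss the plan's own margin.

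The cost is a few sentences and one table column, with no new data or subjects. The drawback for the sponsor is a safety result that looks less favourable than a bare 0%.

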#### 8.0 SURGICAL PROCEDURE

The tympanostomy procedures will take place in a hospital or ambulatory surgery center. The choice of anesthesia drugs for moderate sedation will be up to the attending physicians. The H-TTS will be used to make the myringotomy incision and place the VT. Patients will receive moderate sedation and local anesthetic. Per standard sedation procedure, a patient may be converted to general anesthesia if deemed appropriate by the surgeon.

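### Sedation type and surgeon experience are modelled against conversion across four sites with no site or study term, so a site difference could appear as a sedation association

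*Combined protocol and SAP*

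**What the plan says.** Section 3.1 sets the scale: "A minimum of one hundred nine (109) subjects will be included in the study at 4 sites". One site enrolls prospectively; three supply retrospective data from an earlier moderate sedation study.

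Section 8.0 does not standardise the sedation regimen: "The choice of anesthesia drugs for moderate sedation will be up to the attending physicians". It gives no common criterion for conversion either: "a patient may be converted to general anesthesia if deemed appropriate by the surgeon".

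The regression is described at the end of Section 3.3: "Ad hoc analyses using logistic regression models will be used to assess the relationship between selected parameters and the outcome of conversion to general anesthesia". Ten candidates are listed there: "The pre-specified parameters are age, sex, weight, type of anesthesia/sedation, number of ears treated, surgeon experience, surgery duration, patient movement, anatomy and lack of visualization". The screen is that "those parameters with a p-value less than 0.20 will be included in a multivariable model", followed by stepwise selection: "The nominal p-value for retention in the final reduced model will be 0.05". Site and study appear neither as covariates nor as strata or random effects. Section 4.1 makes these associations part of the conversion endpoint.

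The only planned comparison of conversion between data sources is the Fisher exact test in the poolability text of Section 3.3. It is a 2x2 table in which "the rows consist of the study from which the subjects information came". The data are pooled if p exceeds 0.15. The plan does not say what follows if p is 0.15 or lower.

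**The concern.** Local clinicians choose the sedation drugs and also decide when to convert. Where a site or its anesthesia team favours one regimen and its surgeons convert more or less readily than elsewhere, regimen and conversion will be associated in the pooled data even if the regimen has no influence within any site. A model without a site term cannot tell the two apart. Surgeon experience has the same weakness if it varies mainly between sites.

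The poolability test does not close the gap. It collapses the three retrospective sites into one row, so a high and a low site can offset each other, and passing it adds no site term to the model.

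At stake is how Section 4.1 is read. A regimen retained at the 0.05 level would be listed among the factors associated with conversion, when the data may show only that one site converts more often.

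**Working it through.** **Inputs from the documents.** N = 109 and an expected conversion rate of 15% (Section 3.3, sample size); four sites, one prospective and three retrospective (Sections 1.3 and 3.1); ten candidates, a 0.20 screen and 0.05 retention (Section 3.3). Subjects per site, regimen mix and conversion rate by site are not given, so everything below that uses them is an assumption.

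**The plan's own figure.** The plan gives no figure for the regression. Its one calculated figure is the probability of about 0.80 that the conversion estimate is precise to 6 points. Summing over X ~ Bin(109, 0.15) with z = 1.645, and reading the margin as the Wilson half-width, gives 0.804, which agrees. (Read literally, as bound minus estimate, it gives 0.15; that is a separate wording matter.) The figure that matters here is the number of events: 109 x 0.15 = 16.35 conversions, or 16.35/10 = about 1.6 per candidate, before any site terms.

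**Step 1: a hand example (assumed counts).** Retrospective sites convert 7/20, 2/20 and 2/20; the prospective site converts 6/49. Only the first retrospective site uses regimen Y.

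- Poolability: 11/60 v 6/49, Fisher p = 0.436, above 0.15, so the data are pooled.
- Regimen Y 7/20 v all others 10/89: OR = (7 x 79)/(13 x 10) = 553/130 = 4.25.
- SE(log OR) = sqrt(1/7 + 1/13 + 1/10 + 1/79) = 0.577. The 95% CI is exp(1.448 ± 1.96 x 0.577) = 1.37 to 13.17; z = 2.51, p = 0.012.

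Regimen Y clears both thresholds in the univariable model, yet regimen and site are the same variable. The example is fragile:

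| Conversions at the regimen-Y site | OR | 95% CI | p | Outcome, univariable |
|---|---|---|---|---|
| 7/20 | 4.25 | 1.37 to 13.17 | 0.012 | passes both thresholds |
| 5/20 | 2.63 | 0.79 to 8.81 | 0.12 | passes the screen, above 0.05 |
| 4/20 | 1.98 | 0.55 to 7.09 | 0.30 | fails the screen |

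**Step 2: scenarios with no within-site regimen effect.** The crude OR compares pooled conversion rates. For regimen A, with site size n, conversion rate c and share using A u, pA = Σ(n·u·c)/Σ(n·u); pB uses 1 − u. Worked case: sizes 55 (prospective), 18, 18, 18; conversion 15, 5, 5, 35%; use of A 50, 10, 10, 90%. Then pA = 9.975/47.3 = 0.211, pB = 6.375/61.7 = 0.103, and OR = (0.211/0.789)/(0.103/0.897), which is 2.32 before rounding.

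The ranges below cover three assumed splits of the 109 (55/18/18/18, 80/10/10/9, 30/27/26/26; prospective site first), with 2,000 simulated trials each and likelihood-ratio tests of regimen with and without site indicators. In the first three rows the prospective site converts 15% and uses A in 50%.

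| Scenario (retrospective sites unless stated) | Crude OR | p < 0.05, no site term | p < 0.05, site indicators | Fisher p > 0.15 | False signal and Fisher passed |
|---|---|---|---|---|---|
| Equal mix (50% at every site); conversion 5/5/35% | 1.00 | 6-7% | 6-7% | 88-92% | 5-6% |
| Moderate: conversion 10/10/25%, use 30/30/70% | 1.1-1.4 | 5-9% | 5-6% | 88-92% | 5-8% |
| Strong: conversion 5/5/35%, use 10/10/90% | 1.6-3.5 | 12-65% | 6% | 89-91% | 11-57% |
| Prospective v retrospective only: conversion 10 v 20%, use 20 v 80% | 1.5-1.6 | 11-15% | 6% | 51-60% | 2-3% |

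The equal-mix row shows that site differences in conversion alone do no harm. The strong row shows the exposed case: regimen and conversion vary together among the retrospective sites while the Fisher test usually passes. The last row shows that the test does give some protection when the difference lies between the two sources.

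The simulation tests regimen alone or with site indicators. It does not run the full screen-and-stepwise procedure.

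**The case against.** The strongest case against has five parts.

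1. A reader might infer that site differences will be reported as an effect of the regimen. The documents do not support that. Section 8.0 gives the drug choice to physicians, not to sites, and nothing states how regimens are distributed. Harm needs regimen mix and conversion practice to vary together, and it is small unless clustering is strong. This part stands: the supported word is could.

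2. The models are labelled ad hoc, look for association, and sit beside a statement that no formal hypothesis tests are planned. This stands as to tone. But the same section sets a 0.20 screen and a 0.05 retention level to find statistically significant associations, and Section 4.1 makes them part of an endpoint. Nor do the documents say that regimens will be ranked, or that regimen is the main modifiable factor.

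3. A reader might also infer from Section 10.2 that drugs added during a failing sedation, or the general anesthetic itself, will be recorded as the sedation type. That section covers prospective patients only, lists the reason for conversion as a separate item, and the case report forms are not available here. No such error is shown; an explicit coding rule for the analysis is all that is warranted.

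4. With about 16 conversions over four sites, conditional or exact regression will be imprecise, and surgeon experience may not vary within a site. This stands. It argues for a stratified estimate beside the planned one, not in its place, and for a descriptive treatment of surgeon experience.

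5. Age is described as the only demographic common to both sources, and the documents do not say whether sedation type exists in the retrospective data. A complete-case model that includes sex or weight could shrink to the single prospective site, where between-site confounding cannot arise. That is possible, but the univariable sedation model would still use every site that recorded sedation type. Surgeon experience as a candidate is only a partial proxy for site.

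**Conclusion.** The gap is real and worth correcting, in a limited form. As written, the plan cannot separate a sedation association, or a surgeon-experience association, from site practice, and its poolability test is blind to differences among the three retrospective sites. Whether this distorts the result depends on regimen mix and conversion practice by site, neither of which is given. On the assumed scenarios the consequence runs from none, when the mix is equal, to a crude odds ratio of 3.5 and a 65% false-positive rate, when clustering is strong and sites are of similar size. The hand example with an odds ratio of 4.25 shows that the mechanism works; it is a deliberately unfavourable case and not a forecast. The primary estimate of the conversion rate and the sample size are unaffected.

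**What to change.** In the logistic regression paragraph of Section 3.3:

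- Add a table of sedation type by site, with subjects and conversions in each cell, to be read before any model.
- Report a site-stratified estimate for sedation type (for example conditional or exact logistic regression) alongside the planned unadjusted one.
- Where a regimen is used at only one site, state that its effect cannot be separated from site, and keep it out of the stepwise model.
- Report surgeon experience by site, and state the same limit if it does not vary within site.
- For the analysis, code sedation type as the regimen before any conversion, so that the general anesthetic is not counted as the type.

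The cost is SAP wording, one cross-tabulation and one further estimate. Each subject's site should be identifiable from the data source. Sample size and clinical care do not change. The price is wider intervals, with about 16 expected conversions, and possibly no separate estimate for a regimen used at a single site.
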